9.1.2. Exclusion criteria

Patients meeting any of the following criteria will be excluded from the study:

1. Patients with hospitalization with a primary diagnosis of VTE in the 6-month pre hospitalization period
2. Patients with any OAC administration other than apixaban for apixaban cohort (except warfarin use before apixaban) or warfarin for warfarin cohort during hospitalization

Note: Apixaban cohort patients will be allowed to have warfarin prior to apixaban administration. At this step, we will also report the number of patients that have both apixaban and warfarin use during the hospitalization.

3. Patients with unfractionated heparin or low molecular weight heparin (LMWH) administration after apixaban (for apixaban cohort) or warfarin (for warfarin cohort) administration during hospitalization.

Note: that unfractionated heparin or LMWH prior to apixaban or warfarin will be allowed.

4. With ≥ 1 claim/record with a diagnosis code for atrial fibrillation/flutter in Dx or CDM during the hospitalization and in the 6-month pre hospitalization period
5. With ≥ 1 claim with a procedure code for mechanical heart valve in Dx or CDM during the hospitalization and in the 6-month pre hospitalization period
6. With ≥ 1 claim with a procedure code for inferior vena cava filter in Dx or CDM during the study period
7. With ≥ 1 claim with a diagnosis code or procedure code of pregnancy in Dx or CDM during the study period
8. With use of OAC or PAC (in LRx or Dx) (unless prophylactic) during the 6-month pre-hospitalization period

Note: The OAC or PAC prescription claim will be considered prophylactic if duration of the prescription is ≤ 42 days AND the start date of OAC or PAC occurs within 2 days before or 7 days after knee/hip replacement surgery

OR

Start date of OAC or PAC occurred within 7 days after the admission of a hospitalization associated with 'medically ill' (primary discharge diagnosis; codes provided separately) AND with a ≥ 3 -day length of stay of the hospitalization.

9. With data quality issues (invalid/missing enrollment dates, gender and payer type)

A preliminary attrition table will be provided to the Alliance for review, at which time modifications to the inclusion and exclusion criteria may be considered.

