9.8. Limitations of the research methods

This study will have limitations inherent to observational studies involving claims and hospital charge data, as well as limitations related to the study design. Results from retrospective studies must be interpreted with caution and can only establish associations and not cause-and-effect relationships.

Claims data do not provide as much clinical detail as medical records as they are primarily collected for the purposes of payment. Therefore, there is a potential for miscoding or misclassification (e.g., identification of newly treated VTE patients). There is also the potential for under-coding if they are not captured for billing purposes.

Because these are open-source databases, there is a loss of visibility to healthcare activity/consumption at pharmacies, offices and hospitals that do not participate/contribute to the databases. Pharmacy stability requirements will be applied to the index prescription pharmacy at the patient level. Nevertheless, LRx has high prescription coverage (e.g., 63% of retail pharmacies in the US). Over-the-counter products will not be captured.

Unlike administrative health plan claims data, it is not possible to define periods of continuous enrollment (CE). Only proxies can be implemented based on patient activity and pharmacy stability to provide greater assurance that patient healthcare activity within these databases is captured during the study period. The data also lack information on mortality.

Only patients with a hospitalization or outpatient visit to a hospital in the CDM database are present in the CDM database, therefore potentially representing a more severe population.

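### Exclusion criterion 5 finds mechanical heart valves only through a recent procedure code; criterion 8 catches most earlier implants, and adding diagnosis codes would narrow the small gap that remains in the warfarin cohort

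*Combined protocol and SAP*

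**What the plan says.** Section 9.1.2 lists two exclusions for conditions that could be a separate reason for anticoagulation:

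- Criterion 4 looks for a "claim/record with a diagnosis code for atrial fibrillation/flutter in Dx or CDM", over the index stay and the prior 6 months.
- Criterion 5 applies to patients "With ≥ 1 claim with a procedure code for mechanical heart valve in Dx or CDM during the hospitalization and in the 6-month pre hospitalization" window.

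The window is the same, but criterion 4 uses diagnosis codes and criterion 5 procedure codes. Two further exclusions in the list reach wider. Criterion 6 covers a "procedure code for inferior vena cava filter in Dx or CDM during the study period", and criterion 7 a "diagnosis code or procedure code of pregnancy in Dx or CDM during the study period".

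Criterion 8 removes patients with OAC or PAC use recorded in LRx or Dx in the 6 months before admission, unless the use meets the protocol's definition of prophylaxis.

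Section 9.2.1 does not list valve disease or valve status among the baseline comorbidities. Section 9.6 fits Cox models with warfarin as the reference group. Section 9.8 states that "there is a loss of visibility to healthcare activity/consumption at pharmacies, offices and hospitals that do not participate/contribute to the databases".

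**The concern.** A valve implanted more than 6 months before admission would not be expected to generate an implantation code inside the window. Criterion 5 gives no other route to finding it, such as a diagnosis or status code recording that a prosthetic valve is present. No other criterion in the group combines procedure-only codes with a 6-month look-back, and the protocol gives no reason for that choice.

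A missed patient who was already taking warfarin for a valve would be a prevalent user in a study whose second objective concerns patients who started treatment in hospital. With a long-term indication, such a patient would tend to stay on treatment longer. That these patients would sit mainly in the warfarin cohort, and persist longer there, is a clinical inference and not something the protocol states. If it is right, warfarin persistence would look somewhat longer. Because warfarin is the reference group, the hazard ratio for discontinuation would shift slightly against apixaban. The listed covariates hold nothing that could adjust for this.

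**Working it through.** The protocol states no figure that bears on this point, so there is nothing to reproduce. The check has three parts.

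**1. What each criterion can detect**

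| Criterion | Code type | Window |
|---|---|---|
| 4, atrial fibrillation/flutter | Diagnosis | Index stay and prior 6 months |
| 5, mechanical valve | Procedure only | Index stay and prior 6 months |
| 6, vena cava filter | Procedure | Whole study period |
| 7, pregnancy | Diagnosis or procedure | Whole study period |
| 8, prior OAC/PAC | Drug claim in LRx or Dx | Prior 6 months |

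A valve patient implanted before the window passes criterion 5 but fails criterion 8 if a single non-prophylactic anticoagulant claim is visible. The leak is therefore confined to valve patients with no such visible claim: fills at a non-contributing pharmacy, no fills at all, or fills classed as prophylactic.

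**2. Illustrative size**

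Inputs:

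- Warfarin patients: 18,035 (section 9.4), counted before linkage and the other criteria.
- Unseen share of prior fills: 8% to 37%, the complements of the 92% retail-channel coverage in section 9.3 and the 63% of retail pharmacies in section 9.8. These have different denominators and serve only as a range. Mail (72%) and long-term care (76%) coverage in section 9.3 give 28% and 24%, inside that range.
- Valve prevalence: not in the protocol. Assumed 0.2% to 1.0%, with 3% as a stress value.
- Assumption: criterion 5 misses all of these valves.

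Formula: patients left = 18,035 × prevalence × unseen share.

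| Assumed prevalence | Valve patients | Left at 8% unseen | Left at 37% unseen |
|---|---|---|---|
| 0.2% | 36 | 2.9 | 13.3 |
| 0.5% | 90 | 7.2 | 33.4 |
| 1.0% | 180 | 14.4 | 66.7 |
| 3.0% (stress) | 541 | 43.3 | 200.2 |

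Share of the remaining cohort at 1.0% and 37%: 66.7 / (18,035 − 180.4 + 66.7) = 0.37%. At 0.2% and 8%: 2.9 / (18,035 − 36.1 + 2.9) = 0.016%. At the stress value and 37%: 200.2 / (18,035 − 541.1 + 200.2) = 1.13%.

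**3. Effect on a persistence result**

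Assume, for illustration only, that 50% of other warfarin patients and 10% of valve patients discontinue. The shift is residual share × (50 − 10) percentage points.

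- At 0.37%: 0.0037 × 40 = 0.15 points.
- At 1.13%: 0.0113 × 40 = 0.45 points, so 50.0% becomes about 49.6%.

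**The case against.** The strongest reply is that the protocol already deals with these patients. Long-term anticoagulant users are exactly whom criterion 8 targets, and repeated fills raise the chance that at least one is seen. A reader might infer from criterion 5 alone that patients living with a valve simply stay in the warfarin cohort. Read with criterion 8, the protocol does not support that.

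The 37% unseen share is also very probably too high. Coverage figures describe the market, whereas study patients are selected for visibility. Section 9.1.1 requires at least one LRx claim in the 6 months before admission. Section 9.2 requires, for the outcome cohort, a warfarin claim within 30 days of discharge from a pharmacy that reported in each of the preceding 6 months. To affect persistence, a valve patient needs a visible claim for some drug before admission, no visible anticoagulant claim in those 6 months, and then visible warfarin at a stable pharmacy. A change of pharmacy could produce this, but it is a narrow path.

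Three further points stand. Section 9.4 says its counts do not represent the final study numbers. The valve code list is not in the protocol, so a reader who infers that nearly all existing valves are missed cannot confirm it. And section 9.8 already names misclassification of newly treated patients as a limitation, though without mentioning valves.

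These points reduce the size of the leak. They do not remove the mismatch. The pre-admission LRx claim may be for any drug, the stability rule covers only the index pharmacy, and criterion 8 works only through fills that the data capture. Criterion 5 could provide a check that does not depend on fills, but as written it does not do so for earlier implants.

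**Conclusion.** The point holds in a limited form. Criterion 5 by itself detects recent valve procedures and not earlier implants. Criterion 8 removes most of the patients it misses, leaving valve patients with no visible anticoagulant claim in the 6 months before admission. This is probably well under 1% of the warfarin cohort, with an illustrative upper bound of about 0.4% for assumed prevalence of 0.2-1.0% and unseen fills of 8-37%. Only the stress value of 3% prevalence, combined with the 37% unseen share, takes it just above 1%.

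The likely direction is towards longer warfarin persistence, and no listed covariate corrects for it. On the assumed discontinuation figures the shift is about 0.15 percentage points at the 0.4% bound. A reader might infer that the apixaban-warfarin models are materially biased; nothing in the protocol or in these figures supports that. This is a cheap improvement.

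**What to change.** Reword criterion 5 so that a patient is excluded for either a diagnosis code (including presence-of-valve status) or a procedure code for a mechanical or prosthetic heart valve, in Dx or CDM, in the index stay or in the 6 months before admission. State 'or' between the two periods: the present 'and', taken literally, would require a code in both, and the same wording appears in criterion 4. Report the number removed in the attrition table. Section 9.1.2 already provides for changes to the criteria after the preliminary attrition table is reviewed.

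The cost is a longer code list for one criterion. If the codes do not separate valve types, a few patients with non-mechanical prosthetic valves will also be excluded. Diagnosis codes share the open-source visibility loss and possible under-coding, so the change narrows the gap without closing it completely.

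Keep the 6-month window. Searching all earlier data is a trade-off: with data from July 2017, the look-back would run from 6 months for a January 2018 admission to over 5 years for late 2022, so ascertainment would vary with calendar time.

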9.1. Study period and study design

The analysis will be conducted using data from 01 July 2017 through 31 December 2022 or the latest available data at the time of extraction (i.e., the *study period*). Figure 1 illustrates the study schematic for this project. The study cohorts will be identified during a selection window from 01 January 2018 to 30 November 2022. The date of the first treatment with apixaban or warfarin during the hospitalization will be flagged. Based on this treatment during the VTE hospitalization, patients will be classified into the apixaban and warfarin cohorts. Patients will be required to have medical and pharmacy activity during the 6 months prior to the admit date of the hospitalization (pre hospitalization period) and 1-month (minimum) from the discharge date of the hospitalization (post hospitalization period). The date of the first outpatient prescription for apixaban or warfarin on or within 30 days after discharge date from the hospitalization will be termed as ‘treatment index date’.

Figure 1. Study Period

*Latest available data at the time of extraction will be utilized for this study

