9.1.1. Inclusion criteria

Patients must meet all of the following inclusion criteria to be eligible for inclusion in the study:

1. Patients with an inpatient hospitalization with admit date and discharge date between 01 January 2018 and 30 November 2022 (selection window) in CDM with a primary diagnosis of VTE

Note: The admit date of the first hospitalization with primary diagnosis of VTE during the selection window will be flagged. Only patients with overnight stays with discharge date after the admit date (to confirm inpatient stay with overnight admission) will be included in the study.

Note: Number of patients who died during hospitalization (identified from discharge disposition measure) will be reported and these patients will be excluded from the study.

2. With evidence of receiving apixaban or warfarin during the hospitalization

Note: The date of the record with first apixaban or warfarin administration during the hospitalization will be flagged as the start of apixaban or warfarin treatment. Patients will be assigned to the apixaban or warfarin cohort based on this treatment received during hospitalization.

3. With linkage to LRx between 01 July 2017 and 31 December 2022 (i.e. study period)
4. With linkage to Dx during the study period
5. With activity in the 6 months prior to the admit date of hospitalization, defined as ≥ 1 claim in Dx and ≥ 1 prescription claim in LRx (pre hospitalization period)
6. With activity in the 1-month after the discharge date of hospitalization, defined as ≥ 1 claim in Dx and ≥ 1 prescription claim in LRx (variable post hospitalization period)
Note: Patients will have a minimum 1-month post discharge period (to capture outpatient treatment)
7. With age ≥ 18 years on apixaban or warfarin administration date during index hospitalization

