9.2. Variables

[figure not shown]
From the final sample, the following measures will be reported (Figure 2):

1. Patients with a claim for the respective treatment (apixaban for apixaban cohort or warfarin for warfarin cohort; using NDC from LRx) as their first post-discharge outpatient treatment (on or within 30 days following discharge i.e. discharge date or ≤ 30 days after discharge date) (n, %). These patients will comprise the analytic cohort for outcomes assessment.

- a. The date of the first post-discharge outpatient prescription claim in LRx (apixaban or warfarin) will be defined as the ‘treatment index date’ for patients in both cohorts respectively.
 - b. Patients will be required to have pharmacy stability during the 6-month period preceding the treatment index date, defined as consistent reporting of data in each month from the pharmacy associated with the treatment index date in LRx to ensure continuous visibility within LRx. The number of patients excluded due to lack of stability will be reported (n, %)
 - c. Patients with recurrent VTE, major bleeding, or CRNM bleeding between the discharge date and the treatment index date will be excluded. The number of patients excluded due to these reasons will be reported (n, %).
 - d. Patients will be followed from the treatment index date until the earliest of last prescription, last patient medical claim, end of pharmacy stability, or end of study period using the Dx/Rx databases.
2. Patients with OAC (warfarin, apixaban, rivaroxaban, dabigatran, or edoxaban) other than the respective inpatient treatment as their first outpatient prescription claim (on discharge date or within 30 days of discharge) (NDC codes from LRx; n, %). These patients will be captured as having switched from inpatient therapy and will not be further evaluated for outcomes.
 3. Patients with no post-discharge outpatient prescription claim for any OAC (on or within 30 days of discharge) (NDC from LRx; n, %)

All study outcomes will be evaluated for the apixaban and warfarin cohorts.

Figure 2. Study Flow

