9.2.2. Outcome measures

The following outcome measures are assessed post-discharge, and will be measured during the variable post-index period starting on the treatment index date for the apixaban and warfarin cohorts.

Treatment patterns

- Persistent days (mean, SD, median, IQR, min, max) will be reported for patients until they discontinue, switch or end of follow-up based on definitions below
- Patients discontinuing outpatient treatment of apixaban or warfarin, respectively (NDC codes from LRx; n, %)

Note: Discontinuation will be defined as the occurrence of a ≥ 30 day gap from the run-out of days' supply of the treatment (post-discharge) index prescription (i.e. apixaban or warfarin) to the date of the next claim for the respective therapy or with no other claims for the respective therapy. The date of the discontinuation will be defined as the last day of the days' supply of the last filled prescription.

- Time (in days) from treatment index date to discontinuation date (mean, SD, median, IQR, min, max)

Note: Kaplan-Meier (KM) curves will be generated to measure median time (and 95 % CI) to discontinuation.

- Patients switching to an OAC other than apixaban or warfarin, respectively (switched) (NDC codes from LRx; n, %)

Note: Patients will be considered to have switched if they filled a prescription for OAC other than apixaban or warfarin, respectively (identified through NDC codes in LRx) or for PAC within 30 days before or after the run out date of index treatment. The date of the switch will be defined as date of the prescription of such a therapy (OAC or PAC).

- Time (in days) from treatment index date to switch date, defined as the date of the first claim for the new OAC or PAC (mean, SD, median, IQR, min, max)

Note: KM curves will be generated to measure median time (and 95 % CI) to switching

Clinical Outcomes

The following clinical outcomes will be assessed during the time patients are persistent with their respective index apixaban or warfarin treatment (treatment index):

- Patients with ≥ 1 hospitalization for recurrent VTE (ICD-10 codes in CDM; n, %)
- Incidence rate (IR) of recurrent VTE (per 100 patient years)
 - The date of the first observed event will be flagged. The numerator for IR will be the number of patients with the event of interest and denominator will be the ‘at risk’ period i.e. the time to first event. The 95% confidence intervals (CI) will also be reported.

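### Exclusion criteria 6 and 7 remove patients for IVC filter or pregnancy codes recorded after the treatment index date, and the filter rule can delete counted outcome events

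*Combined protocol and SAP*

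**What the plan says.** Criterion 6 in Section 9.1.2 excludes patients "With ≥ 1 claim with a procedure code for inferior vena cava filter in Dx or CDM during the study period". Criterion 7 excludes patients "With ≥ 1 claim with a diagnosis code or procedure code of pregnancy in Dx or CDM during the study period". Section 9.1 fixes the period: "The analysis will be conducted using data from 01 July 2017 through 31 December 2022", or later if more data are available at extraction.

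The other clinical exclusions close earlier. Criterion 5 looks for a "mechanical heart valve in Dx or CDM during the hospitalization and in the 6-month pre hospitalization period", and criterion 4 (atrial fibrillation or flutter) has the same window. Criteria 1 and 8 look only at the six months before admission.

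Time zero is the first outpatient apixaban or warfarin claim, on or up to 30 days after discharge. Section 9.2, item 1d, states: "Patients will be followed from the treatment index date until the earliest of last prescription, last patient medical claim, end of pharmacy stability", or the end of the study period if that comes first. Item 1c deals with events before time zero, and its window closes at the index date: "Patients with recurrent VTE, major bleeding, or CRNM bleeding between the discharge date and the treatment index date will be excluded".

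Section 9.2.2 states: "The following clinical outcomes will be assessed during the time patients are persistent with their respective index apixaban or warfarin treatment". Recurrent VTE and major bleeding are inpatient stays with a qualifying primary diagnosis, identified in CDM. The incidence rate divides patients with the event by time at risk to the first event.

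**The concern.** Eligibility should be decided by what is known at or before time zero. Under criteria 6 and 7, a code recorded months or years into follow-up, or after a patient's own follow-up has ended, removes that patient retrospectively.

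For the filter rule, removal can be tied to the outcome. If a patient is readmitted with a counted recurrent VTE or major bleed and has a filter code in that stay or later, the event leaves the numerator and the person-time leaves the denominator. This differs from censoring, which would keep the follow-up and the event up to the code. For pregnancy the point is narrower: a later code discards valid earlier follow-up.

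At stake are the event proportions and incidence rates of the secondary objective (Section 8). The apixaban versus warfarin hazard ratios for clinical events (Section 9.6) may also be distorted if the deletion differs by cohort. Section 9.8 does not list this as a limitation.

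**Working it through.** The plan gives no figure to reproduce: it states no filter, pregnancy or event frequency. The dates below come from the documents. Every frequency is an assumption.

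**Step 1: how far the rule looks forward.** Take study end as 31 December 2022. Admission can be no earlier than 01 January 2018, and Section 9.1.1 admits "Only patients with overnight stays with discharge date after the admit date", so the earliest discharge is 02 January 2018. The latest is 30 November 2022.

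- Discharged 02 January 2018: 1,824 days in which a later code excludes the patient.
- Discharged 30 November 2022: 31 days.
- Counted from the treatment index date, the minimum is 1 day (discharged 30 November 2022, indexed 30 days later on 30 December 2022).

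The calendar window is the same for everyone, but its post-discharge part is not. With an assumed code rate of 1 per 100 patient-years, the share excluded, 1 − exp(−0.01 × years), is 4.9% for the earliest discharge (4.99 years) and 0.08% for the latest (0.08 years).

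**Step 2: event proportions.** Let r be the true risk, f the share of patients with a counted event who are removed by a later filter code, and g the same share among event-free patients. A filter code tied to an event after persistence has ended belongs in g, because that event is not counted.

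Reported risk = r(1 − f) / [r(1 − f) + (1 − r)(1 − g)], with r = 0.05 and g = 0.005 assumed.

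| f | Calculation | Reported risk | Relative understatement |
|---|---|---|---|
| 0.5% | 0.04975 / 0.99500 | 5.00% | none |
| 1% | 0.0495 / 0.99475 | 4.98% | 0.5% |
| 2% | 0.0490 / 0.99425 | 4.93% | 1.4% |
| 5% | 0.0475 / 0.99275 | 4.78% | 4.3% |
| 10% | 0.0450 / 0.99025 | 4.54% | 9.1% |

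The proportion is biased downward when f > g.

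**Step 3: incidence rates.** Assume mean at-risk time of 0.25 years for event patients and 0.5 years for event-free patients. Time per patient is T = 0.05 × 0.25 + 0.95 × 0.5 = 0.4875 years, so the true rate is 0.05 / 0.4875 = 10.26 per 100 patient-years. Deleted time is D = 0.05 × f × 0.25 + 0.95 × 0.005 × t, where t is the mean at-risk time of deleted event-free patients. The reported rate is 0.05(1 − f) / (T − D). It is too low if and only if f > D/T.

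| f | t (years) | D/T | Reported rate |
|---|---|---|---|
| 1% | 0.5 | 0.51% | 10.21 |
| 1% | 1.0 | 1.00% | 10.26 |
| 1% | 1.5 | 1.49% | 10.31 |
| 5% | 0.5 | 0.62% | 9.80 |
| 5% | 1.0 | 1.10% | 9.85 |
| 5% | 1.5 | 1.59% | 9.90 |

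At f = 1% the direction changes with t. At f = 5% the rate is understated throughout this range.

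**Step 4: hazard ratios.** With rare events, similar deletion in both cohorts leaves the ratio roughly unchanged and unequal deletion distorts it. The documents do not allow a direction or size to be stated.

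**The case against.** The strongest case against accepts the wording and attacks the weight given to it. Every frequency above is assumed. At f of 1% to 2% the proportion is understated by only 0.5% to 1.4%, and at f = 1% the sign of the rate bias is undetermined. The 9.1% figure needs event patients to carry later filter codes twenty times as often as event-free patients, and nothing in the documents supports that. No effect on the primary treatment-pattern endpoint is quantified, and the pregnancy rule can be read as a population restriction. All of this stands as a limit on what is claimed. None of it makes selection on future codes sound.

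A second argument is that these are open databases without continuous enrolment (Sections 9.3 and 9.8). A filter placed at a non-contributing hospital, or before July 2017, might first show as a later code, so a whole-period search could find more existing filters. The protocol gives no such rationale. The trade-off is real but does not justify deleting events that precede the code.

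Third, Section 9.1.2 allows the criteria to be changed after a preliminary attrition table is reviewed. That step is optional and does not split codes by timing, so it would not by itself reveal the problem.

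**Conclusion.** The concern holds. Nothing in the document narrows criteria 6 and 7 to time before the treatment index date, so membership of the outcomes cohort depends on later codes. The filter rule can delete a counted recurrent VTE or major bleeding event along with its person-time. That much follows from the text with high confidence.

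The size of the bias cannot be computed from the documents. Under the stated assumptions (r = 5%, g = 0.5%), the relative understatement of event risk runs from none at f = 0.5% to 9.1% at f = 10%, and incidence rates may move in either direction. No size is claimed for hazard ratios or for pregnancy. The change should be made because the rule builds in an avoidable bias that is cheap to remove.

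**What to change.** Keep the look-back start of 01 July 2017 and move only the end of the window. In criteria 6 and 7, replace the reference to the study period with: *from 01 July 2017 through discharge from the index hospitalization (through the treatment index date for the outcomes cohort)*. The extension covers the up to 30 days between discharge and index, as item 1c already does for VTE and bleeding.

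Retain patients whose first filter or pregnancy code falls after that date, with follow-up and events up to the code at minimum. Show results with and without censoring at the code, treat both codes the same way, and name in advance which analysis is the main one. CDM diagnoses carry no day stamp (Section 9.3), so state that an event in the same stay as the code counts before censoring. Report by cohort how many patients the present rule would remove solely for post-index codes; this would show how much the issue matters.

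The cost is wording edits to criteria 6 and 7 and items 1c and 1d, one attrition row per criterion by cohort, and a second run of the clinical-outcome proportions, rates and Cox models. No new data are needed. Three downsides should be acknowledged: censoring at the code may be informative, the uncensored analysis includes some follow-up after a code, and an existing filter first recorded late would no longer be excluded.
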